## DOCUMENT HISTORY

VERSION	DATE	DESCRIPTION
Version 1.0	09-30-2024	Initial Release
Version 2.0	02-05-2025	Edits made to protocol to reflect updated changes.

## 1.1. Synopsis

**Title:** Post Operative Skin Approximation with Cyanoacrylate based Wound Closure Adhesives

**Study Description:** The OptiClose surgical adhesive system combines a liquid adhesive with a self-adhering mesh for the closure of surgical incisions and simple lacerations. It acts as a demonstrated non-invasive alternative to skin sutures and staples. The OptiClose and Dermabond topical skin adhesives combine a self-adhering, pressure-sensitive adhesive (PSA), polyester-based mesh (for incisions requiring a mesh), as well as a simple non mesh application system (for incisions that do not require a mesh) for temporarily adjoining the approximated skin edges of an incision, and a 2-octyl cyanoacrylate liquid adhesive formulation for final skin closure. By sparing long intracutaneous sutures, wound closure time is significantly reduced and wound edge ischemia potentially diminished. The purpose of this study is to conduct a two-arm, prospective, randomized control trial by which participants will be randomly assigned to either receive the Dermabond wound closure adhesive or the OptiClose wound closure adhesive in participants undergoing the closure of any subcutaneous tissue following surgical site incisions.

**Phase:**

**Objectives:** *Primary objective:* To determine the effectiveness of the OptiClose surgical adhesive.

*Secondary Objective(s):* Secondary outcomes include:

- The incidence of any surgical site infections (SSI).
- The incidence and extent of acute inflammatory reactions is documented by

the International Contact Dermatitis Research Group (ICDRG) grading system following application until second follow up visit.

- Optimal cosmesis score (Modified Hollander Score)
- Application/Dry time - liquid adhesive is no longer wet to the touch.
- Number of applicator tubes used of each product

**Endpoints:**

*Primary Endpoint:* Incidence of wound edge apposition without dehiscence or need of re-approximation following wound closure.

*Secondary Endpoint:* Secondary endpoints include:

- Surgical Site Infections (SSIs) (criteria defined by the CDC), if applicable
- Inflammatory reactions as calculated by the International Contact Dermatitis Research Group (ICDRG) grading system (see appendix), if applicable.
- Cosmesis as assessed by the Modified Hollander score (see appendix).
- Dry time as objectively measured by an observer/end user.
- Number of applicator tubes/mesh used.

**Study Population:**

Participants will be patients undergoing a skin closure of a full thickness surgical incision. For the products tested in this study, a total of 60 participants will be required to complete the study, 30 in each group. Enrollment will continue until the study from the evaluable number of participants (60) is completed.

**Inclusion Criteria:**

Individuals who meet all the following criteria will participate in this study:

- Healthy individuals  $\geq 18$  years of age.

- Are able to understand and willing to carry out instructions for this study.
- Full thickness surgical incision requiring subcutaneous closure.

Exclusion criteria:

Individuals who meet any of the following criteria will not be allowed to participate in this study:

- Known sensitivities/allergies to the ingredients contained in the products. Individuals with a self-reported Type IV hypersensitivity reaction to cyanoacrylates (namely acrylates).
- Individuals with a history of incisional site closure using a surgical glue.

**Description of Sites/Facilities Enrolling Participants:**

The study will be conducted in Nadora Health in Johnstown, Colorado.

**Description of Study Intervention:**

This prospective study compares the use of OptiClose and Dermabond in the closure of subcutaneous tissue following surgical site incisions. The study has two separate arms. In the first arm, the incision site will large enough to require the use of a mesh, and participants will be randomized into the OptiClose Secure group or the Dermabond Prineo group. In the second arm of the study, the incision site will be small enough not to require a mesh and will use only glue, and participants will be randomized into the OptiClose Rapid group or the Dermabond Advanced group. In both arms of the study, participants will be assessed at three different time points following the surgical procedure: immediately after application following skin closure, and two subsequent visits. These assessments within this study will investigate the cosmesis score, presence of

possible dehiscence or allergic reactions, dry time, and ease of application.

At the conclusion of the final assessment visit (at the end of the final visit), the participants will be dismissed from the study. Participants are free to withdraw from the study, and the principal investigator may also remove the participant if any issues arise that preclude them from continuing.

**Study Duration:**

Study duration is approximately 4-6 months.

**Participant Duration:**

The study will take approximately 4-6 weeks to complete.

**1.2. Schedule of Activities (SOA)**

	Pre-Op	Post Op	Post Op Follow Up 1	Post Op Follow Up 2
Informed Consent/Subject Enrollment	x			
Product Application to surgical site		x		
Dry time recording (with stopwatch)		x		
Number of applicator tubes used		x		
Circulating Nurse notes assessment for adverse events related to allergic reactions. IF applicable, preforms the International Contact Dermatitis Research Group (ICDRG) grading system		x	x	x
Incidence of Surgical Site Infection (SSIs). If applicable performs the CDC criteria for SSI.		x	x	x

Incisional Site Wound Dehiscence Check (inspection of wound edge approximation).			X	X
Incisional Site Cosmesis Score Check using Modified Hollander Scale			X	X
Incisional Site Photos*		X	X	X
Subject Dismissal				X
*Only applies to participants who have consented to incisional site photos.				

## 2. INTRODUCTION

### 2.1. Background & Rationale

Closure of surgical site incisions in orthopedic spine procedures may include multiple skin layers. Depending on the depth of the incision, suturing of the adipose layer, dermis, subcutaneous, and epidermal layers may be required. Wound closure of the subcutaneous layer may be accomplished by using different modalities such as staples, sutures, or topical skin adhesives. The decision to use one modality over another is largely based on surgeon preference and the area of the body. Topical skin adhesives, such as Opticlose (Medline Industries, LP) and Dermabond (Johnson & Johnson) are ideal for approximating and adjoining opposing skin edges together from lacerations or incisions. This study will evaluate the durability of the Opticlose topical adhesive regarding its ability to hold wound edges together without dehiscence or need for re-approximation following wound closure. The two arms of the study will entail the comparison of participants randomized into either the OptiClose (Secure and Rapid) groups or the Dermabond (Prineo and Advance) groups for the two incision site lengths (incisions large enough to require a combination of mesh and glue or those small enough to require glue only). Recruitment will continue until a minimum of 30 evaluable participants are enrolled and randomized into each group for a particular incision length. In total, 60 participants will be needed to complete the entire study.

### 2.2. Study Products (For this round of testing)

The following SKUs will be used in this study:

***OptiClose Rapid:*** MSC091050

***OptiClose Secure:*** MSC091060 (22 cm)

***Dermabond Advanced:*** ETHDNX12

***Dermabond Prineo:*** J-JCLR222US (22CM)

## **2.3. Risk/Benefit Profile**

### **2.3.1 Potential Study Risks**

This study entails minimal risk to study participants for the Opticlose approximation, which includes commercially available products that can be used in the clinical settings and are designated for use as per the study design. There is a possibility of minor skin irritation and redness, sensation of heat and discomfort, or wound dehiscence. However, the magnitude of this should be no greater than what occurs through normal use of the currently marketed topical skin adhesives. The topical adhesives will only be applied to area(s) of surgical incision which should further minimize risk. Each product used in this study would have been tested for its biocompatibility for dermal irritation and within acceptable parameters of the International Organization for Standardization (ISO) 10993-10 requirements. A small but potential risk of allergic skin reaction may occur as a known risk with use of acylate based wound closure devices.

### **2.3.2 Potential Study Benefits**

This study is for research purposes only. There is no direct benefit to the participant. Information learned from the study may help expand the repertoire of topical adhesives used to treat lacerations and surgical incisions.

### **2.3.3 Assessment of Potential Risk/Benefit Profile**

The potential of learning about durability and of Medline's OptiClose outweighs the potential of acquiring a potential superficial skin irritation. This knowledge will help validate the durability of Medline's OptiClose topic adhesive, which may be comfortably used in the clinical and home settings as indicated.

## **3. END OF STUDY DEFINITION AND STUDY DISCONTINUATION**

A participant will be deemed to have successfully completed the study upon completion of all protocol and study procedures. This study may be suspended or prematurely terminated if there is sufficient reasonable cause. Written notification, documenting the reason for study suspension or termination, will be provided by the suspending, or terminating party to the IRB. If the study is prematurely terminated or suspended, the PI or study staff/ personnel will promptly inform the IRB and will provide the reason(s) for the termination or suspension.

Circumstances that may warrant termination or suspension include, but are not limited to:

- Determination of unexpected, significant, or unacceptable risk to participants as determined by adverse events review.

- Insufficient compliance to protocol requirements.
- Data that is not sufficiently complete and/or valuable.

Study may resume once concerns about safety, protocol compliance, and data quality are addressed, and satisfy the IRB.

## **4. RECRUITMENT STRATEGY**

### **4.1 Strategies for Recruitment**

This is an external study to be conducted with external volunteers. As a result, email, and other forms of electronic or physical recruitment methods will be sent by the Clinical Research team. It is a first come, first serve volunteer opportunity. Once the potential participants respond stating their eligibility based on the parameters outlined in the recruitment tools, they will be further evaluated on their first visit. Information regarding logistics for early participant withdrawal from the study and replacement of participants detailed in Section 8: Statistical Considerations.

## **5. INFORMED CONSENT, VERIFICATION, AND ELIGIBILITY**

### **5.1 Visit 1: Informed Consent & Screening**

#### **5.1.1 Informed Consent**

The study will take place at Nadora Healthcare. The study staff will obtain informed consent from the participant prior to participant activities. Consent will be obtained from all participants and documented on an Informed Consent form (ICF) that has received approval from an IRB/Ethics Committee. The signed ICF must be written in accordance with Good Clinical Practices (GCP) and Good Documentation Practices (GDP) and must comply with all elements required by United States (U.S.) Food and Drug Administration (FDA) 21 CFR 50.25 and International Conference on Harmonization (ICH) 4.8, state and local regulations, and additional elements relevant to specific study situations (including a statement that Medline Industries, LP. and relevant authorities have access to participant records). A copy of the signed consent will be given to each participant.

#### **5.1.2 Verification and Eligibility**

Following informed consent, the participants will undergo screening based on the inclusion/exclusion criteria detailed in the synopsis (section 1.1) and will receive a unique screening number that will be recorded in the Participant Screening Form (PSF). The reason for participant exclusion will be documented in this form.

Participant responses to screening questions and demographic information will be documented in the Participant Screening Form. Potential participants who satisfy all inclusion/exclusion criteria for the study will be enrolled in the study. Once the participant is enrolled, participants will proceed to the activities described in Section 6.1 where they

will be assigned a unique Participant Identification (PID) at the start of their first study visit activity.

## **6. STUDY PROCEDURES AND ASSESSMENTS**

### **6.1 Participant Screening and Informed Consent**

The pre-visit may take up to 30 minutes. Study staff will screen potential participants and obtain informed consent during this time as described in Section 5.

Participants will be randomized depending on the predicted incision size. If the incision site is large enough to require the use of the mesh and glue combination, participants will be randomized into the OptiClose Secure group or the Dermabond Prineo group. If the incision site is determined to be small enough that it does not require a mesh, participants will be randomized into the OptiClose Rapid group or the Dermabond Advanced group.

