### **6.2 Post-operative Application of Surgical Site Adhesive**

After the completion of the surgical procedure the surgical site will be prepared in a standard fashion using appropriate layered closure. During this time, the products (Opticlose or Dermabond), will be applied to the surgical site incision. Following the application of the products, the time the products take to dry on the surgical site will be recorded using a stopwatch.

For the mesh group, the stopwatch will begin when the package is opened and once the mesh is laid down for initial application. Once the mesh is appropriately applied, the first time stamp will be recorded. The stopwatch will begin again once the glue has been opened and will stop once the glue has sufficiently covered the mesh for a second time stamp. The stopwatch will then start again, and the applicator will touch the application site at 15 second intervals until no glue is detected on the gloved finger. Once dry, the third and final time stamp will be recorded.

For participants assigned to the glue only group, the stopwatch will begin once the glue has been opened and will stop once the target area has been sufficiently covered for the first time stamp. The stopwatch will begin a second time and the applicator will touch the application site at 15 second intervals until no glue is detected on the gloved finger. Once dry, the second time stamp will be recorded.

The number of applicator tubes used when applying the various products will also be recorded during the product application.

Throughout this process, the circulating nurse will be assessing the participants for potential adverse events related to any surgical site infections or any signs of allergic skin

reactions. If an allergic reaction is detected the assessment will include an International Contact Dermatitis Research Group (ICDRG) grading system (see appendix). Following the completion of the assessment, the participants will be allowed to leave and follow up in their next office visits.

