### **8.2 Randomization**

The order of products tested first or second will be randomly assigned according to a randomization table developed by the biostatistics team. We will conduct a two-arm, prospective, unblinded, randomized prospective control trial by which participants will be randomly assigned to either receive treatment A: the Dermabond wound closure adhesive or the treatment B: OptiClose wound closure adhesive in participants undergoing the closure of any subcutaneous tissue following surgical site incisions. After assignment to treatment arm per incisional length requirements, participants will be randomized using

simple randomization, with 15 participants designated to receive Opticlose and 15 to receive Dermabond. Participants will be patients undergoing a skin closure of a full thickness surgical incision. For the products tested in this study, a total of 60 participants will be required to complete the study, 30 in each incisional length group. If a participant is unable to complete the study, the participant will be replaced such that the new participant will be assigned to the randomization cohort of the replaced participant.

Enrollment will continue until the study from the evaluable number of participants (60) is completed.

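### Allocation is made before surgery on a predicted incision size, with no concealed or delayed reveal and no rule for a wrong prediction

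*Combined protocol and SAP*

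**What the plan says.** Section 6.1 covers screening and consent before surgery. It opens with "The pre-visit may take up to 30 minutes" and its next paragraph says: "Participants will be randomized depending on the predicted incision size". A large predicted incision leads to randomisation between the two mesh products, OptiClose Secure and Dermabond Prineo. The glue-only products, OptiClose Rapid and Dermabond Advanced, are used "If the incision site is determined to be small enough that it does not require a mesh". No length threshold separates the two categories.

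Section 6.2 gives the later steps: "After the completion of the surgical procedure the surgical site will be prepared in a standard fashion using appropriate layered closure". The adhesive is applied during this stage.

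Section 8.2 describes a "two-arm, prospective, unblinded, randomized prospective control trial" and sets the order of assignment, category first and product second: "After assignment to treatment arm per incisional length requirements, participants will be randomized using" simple randomisation, 15 per brand in each category. On losses it says: "If a participant is unable to complete the study, the participant will be replaced". The replacement inherits the randomisation cohort of the person who left.

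The schedule of activities (1.2) has no row for randomisation. Section 8.3 limits the analysis set to participants with complete data and plans no other set. Section 8.4 leaves the handling of each deviation to be decided before analysis starts.

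**The concern.** Two things are at stake.

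**Knowledge of the product during closure.** The primary endpoint is whether the wound edges stay together without dehiscence or re-approximation. The deeper closure under the adhesive could plausibly influence that. If the team knows which brand will follow, the care taken with that closure can differ by brand, even unintentionally. The adhesive cannot be masked while it is being applied, but the deep closure could be finished before anyone learns the assignment. The plan gives up that protection without giving a reason.

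**Events between allocation and use.** The category is predicted, while the product is used after the true incision is known. If the two disagree, the allocated product belongs to the other category. If surgery is cancelled, a randomised participant never receives a product. The plan does not say whether a mismatched participant keeps the allocated product, changes product or is replaced, or in which 15-person cell that participant is counted.

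**Working it through.** The plan gives no figure on this point: no misprediction rate, no cancellation rate and no size threshold. Its one calculation, the detectable difference in dry time in 8.1, does not bear on when allocation takes place. The check is therefore a comparison of sections, followed by an illustration under a stated assumption.

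**Step 1. Order of events.**

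| Step | Where | When |
|---|---|---|
| Consent and screening | 6.1, schedule 1.2 | Pre-operative visit |
| Category set by predicted size, then product randomised | 6.1, 8.2 | Described in the pre-operative section; exact time and person not given |
| Layered closure | 6.2 | After the procedure |
| Adhesive applied | 6.2 | Same stage |
| Dehiscence check | 6.3, schedule 1.2 | Two follow-up visits |

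Allocation comes before closure on the plain reading of *predicted*. Nothing between the two keeps the assignment hidden.

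**Step 2. How many could be affected.** Inputs: N = 60 (8.2) and misprediction rate q, which is an assumption. Expected number = 60q. Chance of at least one = 1 − (1 − q)^60. Total randomised if every such participant were replaced = 60/(1 − q), rounded up.

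| Assumed q | Expected among 60 | Chance of at least one | Total randomised if all replaced |
|---|---|---|---|
| 2% | 60 × 0.02 = 1.2 | 1 − 0.98^60 = 70% | 60/0.98 → 62 |
| 5% | 60 × 0.05 = 3 | 1 − 0.95^60 = 95% | 60/0.95 → 64 |
| 10% | 60 × 0.10 = 6 | 1 − 0.90^60 = 99.8% | 60/0.90 → 67 |

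So even a low rate makes at least one mismatch more likely than not. The last column is an upper case, because the plan does not say that mismatched participants are replaced.

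**Step 3. What one mismatch does to the comparison.** Suppose one participant allocated to OptiClose Secure turns out to need no mesh and receives OptiClose Rapid. The OptiClose mesh cell goes from 15 to 14 and the OptiClose glue-only cell from 15 to 16. Pooled by brand, 14 + 16 = 30, as before. The brand comparison as randomised is kept, but both 15 v 15 category comparisons are disturbed. If the participant were replaced instead, the cells would be refilled, but the newcomer's brand would be fixed in advance by whom they replace.

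**The case against.** The strongest reply is that much of the harm is inferred.

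- **Early knowledge.** A reader might infer that the surgeon is told the product before closing. The documents do not say so. They say the trial is unblinded and are silent on when the assignment is disclosed. The verb *determined* in 6.1 also leaves some doubt about when size is settled. What stands is that early knowledge is possible and nothing prevents it.
- **Switches and replacements.** A reader might infer that wrong predictions do cause them. No section describes a switch, and 8.2 ties replacement to not finishing the study. A mispredicted participant can still be treated and followed. What stands is the missing rule.
- **Breaking the randomised comparison.** Section 8.2 defines the two treatments by brand, and the primary test in 8.8.1 compares brands. A within-brand change keeps that comparison. Size is predicted before the product is drawn, so wrong predictions have no built-in link to brand.
- **Deciding the primary result.** One could point out that 0 v 4 failures in 30 v 30 gives p = 0.038 on the Pearson chi-square. Fisher's exact test gives 2 × 27,405/487,635 = 0.11 for the same table. Either figure shows only that a sparse endpoint is fragile, not that allocation timing moves any event.
- **Limited gain.** Section 6.2 asks for a standard closure in everyone, and a later reveal leaves the operator unblinded at application and the assessors unblinded at follow-up. This is correct. The change closes one route to bias, not all of them.

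**Conclusion.** The concern holds in a limited form. The plan randomises on a prediction, before the closure that could influence the primary endpoint, in an unblinded trial with no concealed or delayed reveal and no rule for a predicted/actual mismatch. That leaves an avoidable route to performance bias and allows avoidable mismatches and losses after randomisation.

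The size is unknown. The figure of about 1 to 6 participants in 60 rests wholly on the assumed 2% to 10% misprediction rate. It does not count cancelled operations, for which the documents also give no rate. The documents do not support a claim that bias has occurred, that the pooled brand comparison is lost, or that the primary p-value would change.

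This is a cheap improvement to the design rather than a flaw that invalidates the trial.

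**What to change.** 1. In 6.1, keep consent, eligibility and the provisional size estimate at the pre-visit, and remove randomisation from it.
2. In 6.1 and 8.2, state that the concealed allocation (sealed envelope, or a list held by study staff outside the surgical team) is revealed only after the deep layers are closed, from a list stratified by the actual mesh or glue-only category. State who reveals it and that the time is recorded.
3. Add a randomisation row to the schedule of activities (1.2), placed between deep closure and product application.
4. If some participants have already been randomised on predicted size, state how a mismatch is recorded and analysed. Section 8.1 speaks of results in hand; if enrolment has ended, report when allocation was disclosed, and list every mismatch and replacement by brand and category.

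With steps 1 and 2, a cancelled operation or a wrong prediction happens before randomisation and needs no switch or replacement.

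**Cost.** An envelope or list must be opened in theatre, and both products of the category must be to hand. The change does not raise the required 60 participants. It does not remove operator knowledge during application, unblinded assessment at follow-up, or replacement of participants who leave after treatment.
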